## 3.1.1. Study Treatment

See Section 5 for dosage and treatment administration of voxelotor and placebo.

## 3.1.2. Study Assessments

Study procedures and assessments are described in Section 6. The timing for the study procedures and assessments is provided in the SOA (Appendix 1).

Participant safety and tolerability will be monitored during the study using standard measures, including physical examinations, vital signs (including temperature, blood pressure, and pulse rate), clinical laboratory tests, and AE monitoring.

## 3.1.3. Study Endpoints

Target leg ulcer images will be sent for central review (see Section 6.7).

## 3.1.3.1. Primary Endpoint

The primary endpoint will be measured by the proportion of participants achieving resolution of the target ulcer(s),

during the 12-week Randomized Treatment Period.

For participants with more than one target ulcer, all target ulcers must be confirmed resolved in order for the participant to be considered a responder.

## 3.1.3.2. Secondary Endpoints

Secondary endpoints in this study include a comparison of voxelotor and SOC versus placebo and SOC in:

- Time (in days) to resolution of target ulcer(s) up to Week 12
- Change from baseline in total surface area of target ulcer(s) at Week 12
- Incidence of new ulcers by Week 12

## 3.1.3.3. Exploratory Endpoints

Exploratory endpoints include:

- Proportion of participants achieving resolution of target ulcer(s) by Week 24
- Time (in days) to resolution of target ulcer(s) up to Week 24
- Change from baseline in total surface area of target ulcer(s) over time up to Week 24
- Correlation between change in Hb and target ulcer(s) healing at Week 12 and Week 24
- Correlation between change in markers of hemolysis (% reticulocytes, indirect bilirubin, LDH) and target ulcer(s) healing at Week 12 and Week 24

- Change from baseline in PRO HRQOL measures: PROMIS-37 v2.0 Pediatric Profile/PROMIS-43 v2.1 at Week 12 and Week 24
- Change from baseline in pain level linked to target ulcer(s) assessed by VAS at Week 12 and Week 24
- PGI-C score at Week 12 and Week 24
- CGI-C score at Week 12 and Week 24

## 3.1.3.4. Safety Endpoints

The safety endpoints include assessments of AEs, clinical laboratory parameters, physical examinations, and vital signs.

#### 3.1.4. Minimization of Bias

This study uses a double-blind, randomized, multicenter design to minimize bias.

## 3.2. Duration of Study Participation and of the Study

The approximate study duration for an individual participant includes the Screening Period (within 28 days), a Run-in Period of 2 weeks, a Randomized Treatment Period of 12 weeks, an Open-label Treatment Period of a minimum of 12 weeks, and a Follow-up Period/EOS visit (4 weeks [± 7 days] after the last dose of study drug). From Screening through Follow-up, total participation in this study for an individual participant may last from approximately 31 weeks to up to 34 weeks, except for participants who continue to receive voxelotor beyond 12 weeks in the Open-label Treatment Period (see below). Participants will continue to be followed for efficacy and safety through at least the primary endpoint visit (Week 12) regardless of treatment discontinuation.

Participants who have completed 12 weeks in the Open-label Treatment Period may continue to receive voxelotor as long as they continue to receive clinical benefit that outweighs risk as determined by the Investigator or until the participant has access to voxelotor from an alternative source (eg, through a clinical OLE study sponsored by Pfizer, commercialization of the product, or a managed access program).

Participants who choose not to continue voxelotor after 12 weeks in the Open-label Treatment Period will be followed for 4 weeks after the last dose of treatment and instructed to return to the site to complete the EOS visit (Visit 16-B, Appendix 1).

The study will end when the last participant's last visit occurs.

For participants who terminate the study prior to their last visit, refer to Section 3.3.1.

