#### Early Termination Visit

If a participant terminates the study for any reason, this should be documented on the electronic case report form (eCRF) and the assessments for the Early Termination visit should be performed per the SOA (Appendix 1).

Safety and tolerability will be monitored during the entire study using standard measures, including the assessment of AEs, clinical laboratory tests, physical examinations, and vital signs.

Figure 1: Study Schema

Abbreviations: SOC, standard of care

\* Participants who have completed 12 weeks in the Open-label Treatment Period may continue to receive voxelotor as long as they continue to receive clinical benefit that outweighs risk as determined by the Investigator or until the participant has access to voxelotor from an alternative source (eg, through a clinical OLE study sponsored by Pfizer, commercialization of the product, or a managed access program). Participants who do not plan to continue to receive voxelotor from an alternative source should continue to the follow-up period after completing 12 weeks in the Open-label Treatment Period.

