## 3.3.2.2. Early Discontinuation of Study Treatment

Participants may be discontinued from study treatment for any of the following reasons:

- Participant is lost to follow-up
- Adverse event(s)
- Repeated surgical debridement of target ulcer(s) needed to address wound deterioration
- Discretion of the Investigator
- Discretion of the Sponsor
- Pregnancy

The participant should return to the study site for an EOS/Early Termination visit approximately 28 days (±7 days) after the last dose of study treatment, as indicated in the SOA.

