#### 5.7.3. Transfusion

Participants who require initiation of chronic transfusion will be discontinued from study treatment and 28 days later will undergo the EOS/Early Termination visit. Episodic transfusions for acute SCD indications, pre-operative procedures, surgery, or trauma are permitted.

Note: Participants who continue to receive voxelotor beyond 12 weeks in the Open-label Treatment Period (see Section 5.1) may initiate chronic transfusions without being discontinued from study treatment.

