## 5.7.4. Other Therapies

Penicillin prophylaxis and vaccinations are allowed as per SOC.

Other concomitant medications are allowed, unless the restrictions in Section 5.7.5 apply. Permitted concomitant medications include folic acid, L-glutamine, and over-the-counter analgesics, and opioids, which are among the chronic medications commonly taken by participants with SCD. Erythropoietin-stimulating agents (stable dose for at least 4 weeks with no dose modifications planned or anticipated by the Investigator) are allowed.

Participants who are already on malaria prophylaxis therapy may be allowed to participate in the study at the discretion of the Investigator. Participants may also be initiated on malaria prophylaxis therapy during study, at the discretion of the Investigator and as per SOC.

Participants who test positive for acute malaria during the study should be provided SOC treatment and may continue in the study, at the discretion of the Investigator and the Sponsor.

Participants who test positive for acute hepatitis or HIV during the study will be discontinued from study drug and will return for the EOS/Early Termination visit (28 days after the last dose of study drug).

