## 5.8.1. Instructions for Female Participants of Child-Bearing Potential

For female participants of child-bearing potential (post menarche) and sexually active, pregnancy should be avoided by either abstinence from sex/sexual intercourse or the use of highly effective means of contraception for the duration of the study, and for a total period of 30 days after the participant has taken her last dose of voxelotor. Highly effective means of contraception are listed below in Section 5.9. Pregnancy reporting requirements are outlined in Section 1.1.

Female participants who become pregnant during the study will be withdrawn from the study.

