## 7.2. Adverse Event Reporting

## 7.2.1. General

All AEs/SAEs will be recorded from the time the study participant signs the ICF/assent until 28 days after last dose of study drug (EOS/Early Termination). All AEs/SAEs must be recorded on the AE eCRF via the electronic data capture (EDC) system. The Investigator is responsible for evaluating all AEs/SAEs, obtaining supporting documents, and ensuring documentation of the event is complete. Details of each reported AE must include, at minimum, severity, relationship to study treatment, duration, and outcome. All AEs (both serious and nonserious) must be followed until they are resolved or stabilized, or until reasonable attempts to determine resolution of the event are exhausted.

Any participant who experiences an AE/SAE may be discontinued from study treatment at any time, at the discretion of the Investigator. The Sponsor and the contract research organization (CRO)'s Medical Monitor must be notified of the study participant discontinuation.

When a clinically important AE remains ongoing at the end of the active collection period, follow-up by the investigator continues until the AE or SAE or its sequelae resolve or stabilize at a level acceptable to the investigator and Pfizer concurs with that assessment.

For participants who are screen failures, the active collection period ends when screen failure status is determined.

If the participant withdraws from the study and also withdraws consent for the collection of future information, the active collection period ends when consent is withdrawn.

If a participant permanently discontinues or temporarily discontinues study drug because of an AE or SAE, the AE or SAE must be recorded on the eCRF and the SAE reported to Pfizer Safety via Pfizer's Serious Adverse Event Submission Assistant (PSSA).

Investigators are not obligated to actively seek information on AEs or SAEs after the participant has concluded study participation. However, if the investigator learns of any SAE, including a death, at any time after a participant has completed the study, and they consider the event to be reasonably related to study drug, the investigator must promptly report the SAE to the Sponsor via PSSA.

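### Protocol 3.2 promises ulcer follow-up to Week 12 after a treatment stop, but the sections a site acts on when drug is stopped do not carry the promise through

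*Protocol*

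**What the plan says.** The general rule is in Protocol 3.2, repeated in the Synopsis: "Participants will continue to be followed for efficacy and safety through at least the primary endpoint visit (Week 12) regardless of treatment discontinuation".

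The instructions for particular situations read differently:

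- Section 3.3.2.2 opens with "Participants may be discontinued from study treatment for any of the following reasons", includes pregnancy in its list, and then calls the participant back for an "EOS/Early Termination visit approximately 28 days (±7 days) after the last dose of study treatment".
- Section 5.7.3: a participant who needs to start chronic transfusion "will be discontinued from study treatment and 28 days later will undergo the EOS/Early Termination visit".
- Section 5.7.4: a participant found to have acute hepatitis or HIV "will be discontinued from study drug and will return for the EOS/Early Termination visit", again at 28 days.
- Section 3.1 introduces the Early Termination visit with "If a participant terminates the study for any reason".
- Section 7.2.1 records AEs from consent "until 28 days after last dose of study drug (EOS/Early Termination", so the same label marks the end of AE collection.
- Section 5.8.1: "Female participants who become pregnant during the study will be withdrawn from the study".

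Appendix 1 sets visits by week and includes an ulcer assessment at the Early Termination visit. It has no column or footnote for a participant who is off drug but still in the study. A closure first seen at Week 12 is confirmed two weeks later (Appendix 1, footnote u; SAP 2.3.2). SAP 5.3.1 scores participants who leave without confirmed resolution of all target ulcers as non-responders, and SAP 3.2 censors their time to resolution.

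**The concern.** Stopping drug and leaving the study are different events, and 3.2 separates them correctly. The operative sections blur them: a participant who only stops drug is sent to a visit whose name, and whose description in 3.1, belong to study exit. None of these sections refers back to 3.2 or says that ulcer photography continues.

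A site that takes the 28-day visit as the last one loses the Week 12 ulcer status, and a photograph that was never taken cannot be recovered at analysis. The participant then becomes an imputed failure where 3.2 intended an observed outcome. If stopping differs by arm, the primary comparison is biased against the arm that stops more. The safety half of the promise is affected too, since 28 days after an early stop falls before Week 12. The reported type of censoring (SAP 5.2.3) would show missing follow-up but not whether the participant had first stopped drug.

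**Working it through.** **Timing, if the 28-day visit is taken as study exit.** Windows are from SAP Appendix 2.1.

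- Protocol Week 12 window, Day 81-87: last dose + 28 < 81 gives a stop by Day 52. At the ends of the ±7-day allowance the limits are Day 45 (+35) and Day 59 (+21).
- SAP analysis window for Week 12, from Day 78: last dose + 28 < 78 gives Day 49.
- Protocol Week 14 window, from Day 95: last dose + 28 < 95 gives Day 66.

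The 28-day visit includes an ulcer assessment, but a closure first seen there has no later visit to confirm it.

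**The plan's own figure.** Protocol 8.6 gives 40 per arm, a 35-point difference, two-sided 5%, normal approximation and about 90% power. With pc and pv the two healing rates and p̄ their mean, power = Φ{[(pv − pc) − 1.96·√(2p̄(1−p̄)/n)] / √[pc(1−pc)/n + pv(1−pv)/n]}. The placebo rate is not visible, so it is varied. At n = 40, placebo healing of 10, 20, 30 and 40% gives 95.4, 91.4, 89.5 and 90.2%. The stated figure reproduces for 20-40%.

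**Bias.** The documents give 5% dropout but no treatment-stop rate. Assumptions: placebo healing pc = 10-40%, voxelotor pc + 35 points, a fraction s of the voxelotor arm stops and none of the placebo arm, and participants off drug heal at the control rate. A fraction l of the arm is lost and scored as failures.

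- Followed as 3.2 intends: 0.35(1 − s). At s = 0.10 this is 31.5 points.
- With loss: 0.35(1 − s) − l·pc, so the bias is l·pc.
- All stoppers lost, l = s = 0.10: 1.0-4.0 points, leaving 30.5-27.5. That is 0.4-1.6 of 40 participants.
- Only stops by Day 52 lost, stop days assumed even over Day 1-84, l = 0.10 × 52/84 = 0.062: 0.6-2.5 points, leaving 30.9-29.0. That is 0.2-1.0 participants.
- s = 0.05: 0.5-2.0 points if all are lost, 0.3-1.2 if only early stoppers are.

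These are upper bounds, because l·pc does not subtract closures already confirmed before exit.

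**Power with the planned exact CMH test**, s = 0.10 in voxelotor only. One stratum and four equal strata (assumed, as the cut-offs are not visible) agree within 0.6 points.

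| Placebo healing | Followed | Early stoppers lost | All lost |
|---|---|---|---|
| 10% | 88% | 87% | 86% |
| 20% | 79% | 76% | 73-74% |
| 30% | 77% | 71% | 67% |
| 40% | 77% | 69% | 64% |

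Only the fall across a row is due to lost visits. Most of the gap between the first column and 90% comes from the exact test and from stopping itself.

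**Balanced stopping**, 10% in each arm: the difference is 31.5 points whether stoppers are followed or scored as failures. Normal-approximation power is 82-91% followed and 82-92% scored as failures.

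**No true difference**: the exact test rejects 1.7-3.1% without stopping, and 1.6-4.0% with 10% placebo-only stoppers scored as failures. Both stay below 5%.

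**The case against.** The strongest reply is that the rule for this exact case exists and is explicit. Section 3.2 covers participants who stop drug, 6.7 calls for ulcer assessment at each visit, and Appendix 1 schedules visits by week rather than by drug status. A 28-day visit also has an evident safety purpose and can sit alongside the ulcer visits. This stands. A reader might infer that the protocol gives stoppers nothing but the 28-day visit, but no section says so; that inference rests on silence and on the visit's name. What remains is that the visit is labelled as study exit in the sections a site consults, with no pointer back to 3.2.

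On AEs, SAP 6.6.1 plans a listing that includes events more than 28 days after last treatment, and 7.2.1 requires clinically important ongoing AEs to be followed until resolved or stable. That softens the safety conflict but does not extend active collection of new AEs to Week 12.

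On size, 10% one-sided stopping is an adverse assumption; Protocol 1.4 says AEs seldom led to stopping voxelotor. Subtracting earlier confirmed closures under an assumed confirmation rule (the actual rule is not visible) brings the largest figures from 2.48 to 1.8-2.45 points and from 4.0 to 2.1-3.7.

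A reader might also infer that balanced stopping costs power, since scoring 10% of each arm as failures takes 91.4% to 86.0% at 20% placebo healing. That compares with nobody stopping. Against stoppers who are followed (20% versus 51.5% healing, 85.0% by the formula above), nothing is lost.

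On pregnancy, the event should be rare under the contraception rules and requires unblinding (3.4.1.2), so whether efficacy follow-up should continue is debatable.

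**Conclusion.** The point holds as a conflict of instruction between 3.2 and sections 3.1, 3.3.2.2, 5.7.3, 5.7.4 and 7.2.1. Its effect is conditional on a site treating the 28-day visit as exit. The bias is then at most 0.6-2.5 points with early stoppers lost and 1-4 points with all lost, under an assumed 10% voxelotor-only stop rate and 10-40% placebo healing, and about half that at 5%. The associated power loss is 1-2 points at 10% placebo healing and 8-13 points at 40%. Balanced stopping costs essentially nothing. The documents do not support a claim that the primary test is invalid: the bias runs against the arm that stops more, and the null rejection rate stays at or below 4.0%. The non-responder rule in SAP 5.3.1 is confined to loss to follow-up and study dropout and needs no change. The mismatch between 5.8.1 and 3.3.2.2 on pregnancy is real but secondary.

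**What to change.** - Protocol 3.3.2.2, 5.7.3, 5.7.4 and Appendix 1: state that a participant who stops drug keeps the scheduled ulcer assessments through Week 12, and Week 14 confirmation where needed, unless consent is withdrawn. Describe the 28-day visit as an additional safety visit.
- Protocol 7.2.1: record AEs to the later of 28 days after last dose and Week 12, in line with the SAP 6.6.1 listing of later AEs.
- Protocol 5.8.1 and 3.3.2.2: say consistently whether pregnancy stops treatment or ends study participation.
- CSR: report treatment discontinuation separately from study discontinuation by arm. Protocol 8.2 already promises the reasons for both; the illustrative list in SAP 6.5.2 names only study discontinuation. Add the count by arm of primary non-responders who were imputed rather than observed.

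The last subject's last visit was on 22 October 2024 (SAP 2), so the protocol wording now serves the record or a later study, where it would cost a few off-drug assessments at visits already scheduled. The CSR items are one disposition table and one count; drug discontinuations are already required in the eCRF (Protocol 5.1.2).

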#### 3.3. Stopping Rules

#### 3.3.1. Early Discontinuation of the Study

The Sponsor has the right to terminate this study at any time. Reasons for terminating the study may include, but are not limited to, the incidence or severity of TEAEs in this or other studies with voxelotor indicating a potential health risk to participants.

In any instance of early termination of the study, the Sponsor will notify, in writing, the Investigators, regulatory authorities, and Independent Ethics Committees (IECs) and will specify the reason(s) for termination.

## 3.3.2. Discontinuation of Individual Participants

#### 3.3.2.1. Withdrawal of Consent

Participants and/or their caregiver/legal representative will be informed participation is voluntary and that they may discontinue treatment or withdraw from the study at any time and for any reason. Any participant who requests to be withdrawn or whose caregiver/legal guardian requests withdrawal will be withdrawn from the study by the Investigator.

## 3.3.2.2. Early Discontinuation of Study Treatment

Participants may be discontinued from study treatment for any of the following reasons:

- Participant is lost to follow-up
- Adverse event(s)
- Repeated surgical debridement of target ulcer(s) needed to address wound deterioration
- Discretion of the Investigator
- Discretion of the Sponsor
- Pregnancy

The participant should return to the study site for an EOS/Early Termination visit approximately 28 days (±7 days) after the last dose of study treatment, as indicated in the SOA.

#### 3.4. Randomization and Unblinding

#### 3.4.1. Randomization

Randomization will be carried out through an Interactive Response System (IXRS). Permuted blocks within randomization strata will be used. Eligibility of the participant will be confirmed by the Investigator prior to randomization.

## 3.4.1.1. Preventing Unblinding due to Laboratory Assessments

Because knowledge of certain laboratory assessments (Hb, hematocrit, RBC count, total and unconjugated bilirubin, or absolute and % reticulocyte count) may suggest the treatment assignment in the Randomized Treatment Period, these measurements will be redacted to the Investigator.

Results of redacted laboratory tests will be communicated to the Investigator if a participant's absolute reticulocyte count declines to < 80 × 10^9/L, or Hb declines to < 5.0 g/dL, or if the Hb declines ≥ 2 g/dL from Screening. This does not require breaking of the treatment assignment blind. This is to ensure participant safety by allowing the Investigator to monitor for potential bone marrow suppression, as described in HU monitoring guidelines (McGann, 2015; Yawn, 2014). De-identified laboratory results will be available to the Sponsor.

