## 7.2.3. Abnormal Laboratory Values

Only clinically significant laboratory abnormalities will be recorded on the AE eCRF (eg, abnormalities that have clinical sequelae, require study drug dose modification, discontinuation of study treatment, more frequent follow-up assessments, further diagnostic investigation). If the clinically significant laboratory abnormality is a sign of a disease or syndrome (eg, ALP and bilirubin 5 × the ULN associated with cholecystitis), only the diagnosis (eg, cholecystitis) needs to be recorded in the eCRF.

If the clinically significant laboratory abnormality is not a sign of a disease or syndrome, the abnormality itself should be recorded in the eCRF. If the laboratory abnormality can be characterized by a precise clinical term, the clinical term should be recorded. For example, an elevated serum potassium level of 7.0 mEq/L should be recorded as "hyperkalemia."

Observations of the same clinically significant laboratory abnormality from visit to visit should not be repeatedly recorded on the AE eCRF, unless their severity, seriousness, or etiology changes.

Note: Potential drug-induced liver injury (DILI; Hy's law) cases are to be reported as SAEs (Section 7.3). For suggested actions and follow-up assessments in the event of potential DILI, refer to Appendix 2.

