## 7.3. Serious Adverse Events, Serious Adverse Drug Reactions, and Requirements for Immediate Reporting

All SAEs, regardless of causal attribution, must be reported by the Investigator/designee or site personnel within 24 hours of SAE awareness on the AE eCRF and reported to Safety via PSSA. In the event PSSA is not available, paper CT SAE Report Forms will be used to report the SAE and faxed or emailed to Pfizer Safety. The information reported on the paper SAE report form should be entered into PSSA once available.

The Sponsor may request additional information pertaining to the SAE from the investigational site. Follow-up reports must be submitted within 24 hours of awareness as additional information becomes available.

All SAEs regardless of causal attribution must be followed to resolution, stabilization, or until reasonable attempts to determine resolution of the SAE are performed.

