- Participants with AST/ALT and total bilirubin values within the normal range who subsequently present with AST/ALT values ≥ 3 × ULN AND a total bilirubin value ≥ 2 × ULN with no evidence of hemolysis and an alkaline phosphatase value < 2 × ULN or not available.

- For participants with baseline AST OR ALT OR total bilirubin values above the ULN, the following threshold values are used in the definition mentioned above, as needed, depending on which values are above the ULN at baseline:
  - Preexisting AST/ALT baseline values above the normal range: AST/ALT values ≥ 2 times the baseline values AND ≥ 3 × ULN; or ≥ 8 × ULN (whichever is smaller).

 Preexisting values of total bilirubin above the normal range: total bilirubin level increased from baseline value by an amount of ≥ 1 × ULN or if the value reaches ≥ 3 × ULN (whichever is smaller).

Rises in AST/ALT and total bilirubin separated by more than a few weeks should be assessed individually based on clinical judgment; any case where uncertainty remains as to whether it represents a potential Hy's law case should be reviewed with the sponsor.

The participant should return to the investigator site and be evaluated as soon as possible, preferably within 48 hours from awareness of the abnormal results. This evaluation should include laboratory tests, detailed history, and physical assessment.

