In addition to repeating measurements of AST and ALT and total bilirubin for suspected Hy's law cases, additional laboratory tests should include albumin, creatine kinase, direct and indirect bilirubin, gamma-glutamyl transferase, prothrombin time/international normalized ratio, eosinophils (%), and alkaline phosphatase. Consideration should also be given to drawing a separate tube of clotted blood and an anticoagulated tube of blood for further testing, as needed, for further contemporaneous analyses at the time of the recognized initial abnormalities to determine etiology. A detailed history, including relevant information, such as review of ethanol, acetaminophen/paracetamol (either by itself or as a coformulated product in prescription or over-the-counter medications), recreational drug, or supplement (herbal) use and consumption, family history, sexual history, travel history, history of contact with a jaundiced person, surgery, blood transfusion, history of liver or allergic disease, and potential occupational exposure to chemicals, should be collected. Further testing for acute hepatitis A, B, C, D, and E infection, total bile acids, liver imaging (eg, biliary tract), and collection of serum samples for acetaminophen/paracetamol drug and/or protein adduct levels may be warranted.

All cases demonstrated on repeat testing as meeting the laboratory criteria of AST/ALT and total bilirubin elevation defined above should be considered potential DILI (Hy's law) cases if no other reason for the LFT abnormalities has yet been found. Such potential DILI (Hy's law) cases are to be reported as SAEs, irrespective of availability of all the results of the investigations performed to determine etiology of the LFT abnormalities.

A potential DILI (Hy's law) case becomes a confirmed case only after all results of reasonable investigations have been received and have excluded an alternative etiology.

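### The blinded laboratory report withholds total bilirubin and has no liver release trigger, so the protocol's own Hy's law rule cannot be completed from it

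*Protocol*

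**What the plan says.** **Redaction.** Protocol 3.4.1.1 lists the results that could suggest treatment assignment, "Hb, hematocrit, RBC count, total and unconjugated bilirubin, or absolute and % reticulocyte count", and withholds them from the Investigator in the Randomized Treatment Period.

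**Release.** The same section releases the redacted results on three conditions: absolute reticulocytes below 80 × 10^9/L, Hb below 5.0 g/dL, or an Hb fall of at least 2 g/dL from Screening. It gives the reason: "This is to ensure participant safety by allowing the Investigator to monitor for potential bone marrow suppression". On the blind it says: "This does not require breaking of the treatment assignment blind". De-identified results are available to the Sponsor.

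**Liver rule.** For participants with normal baseline values, Appendix 2 asks for evaluation as a potential Hy's law case at "AST/ALT values ≥ 3 × ULN AND a total bilirubin value ≥ 2 × ULN with no evidence of hemolysis", with ALP below 2 × ULN or not available. If bilirubin is already raised at baseline, the criterion is "total bilirubin level increased from baseline value by an amount of" at least 1 × ULN, or a value of 3 × ULN, whichever is smaller. The work-up begins "In addition to repeating measurements of AST and ALT and total bilirubin" and adds further tests.

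**Reporting.** Section 7.2.3 states: "Potential drug-induced liver injury (DILI; Hy's law) cases are to be reported as SAEs". Under section 7.3, SAEs "must be reported by the Investigator/designee or site personnel within 24 hours of SAE awareness".

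**The concern.** A blinding rule and a safety rule in the same protocol pull on the same laboratory value. The site is responsible for recognising, working up and reporting a potential Hy's law case, but the routine report withholds the bilirubin result that completes the definition, along with most of the results that would show or exclude hemolysis. The release triggers were written for marrow suppression and do not cover the liver.

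The stake is participant safety. Followed exactly, the release rule can leave a qualifying bilirubin unseen by the treating Investigator. The bilirubin criterion is not remote in this population: Protocol 1.3.1 says that sickle cell anemia patients with leg ulcers have higher bilirubin and AST than those without. The criterion based on change from baseline may therefore often apply, and an isolated AST rise is harder to read without the hemolysis results. Timing adds to this. After the Week 12 sample most participants start or continue open-label voxelotor, and the next scheduled chemistry is at Week 24.

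**Working it through.** No power, alpha or event figure bears on this point. The check compares what Appendix 2 needs with what 3.4.1.1 hides and releases.

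**Step 1. What the Investigator's blinded report shows**

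| Element needed by Appendix 2 | On the blinded report | Basis |
|---|---|---|
| AST/ALT | Visible | Not in the 3.4.1.1 list |
| ALP | Visible | Not in the 3.4.1.1 list |
| Total bilirubin | Hidden | 3.4.1.1 |
| No evidence of hemolysis | Mostly hidden: Hb, reticulocytes and unconjugated bilirubin withheld; LDH visible | 3.4.1.1, 6.10.2 |

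Section 6.10.2 also collects direct bilirubin, which is not redacted. But total = direct + indirect, and the indirect part is withheld, so the total cannot be rebuilt.

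**Step 2. Whether any trigger can fire on a liver signal**

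The trigger analytes are absolute reticulocytes and Hb. The liver analytes are AST, ALT, ALP and bilirubin. The two sets do not overlap.

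**Step 3. Illustration with assumed values**

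Take normal baseline liver tests and then ALT 6 × ULN, total bilirubin 4 × ULN, ALP 1 × ULN, Hb moving from 8.0 to 8.5 g/dL, and reticulocytes 200 × 10^9/L.

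- Appendix 2 thresholds: 6 ≥ 3, 4 ≥ 2 and 1 < 2, so the AST/ALT, bilirubin and ALP thresholds are all met.
- Release triggers: 200 is not below 80; 8.5 is not below 5.0; the Hb change is 8.5 − 8.0 = +0.5 g/dL, not a fall of 2 g/dL. None fires.

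The bilirubin stays hidden although only the hemolysis question is left to settle.

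**Step 4. Raised baseline bilirubin**

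In multiples of ULN, the threshold is the smaller of (baseline + 1) and 3. For an assumed baseline of 1.5 it is min(2.5, 3) = 2.5. For an assumed baseline of 2.5 it is min(3.5, 3) = 3. In either case the current total bilirubin is needed, and that is the hidden value.

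**Step 5. Size of the exposure**

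Section 6.10 schedules chemistry at Screening, Day 1, Week 12, Week 24 and EOS/Early Termination. Only Week 12 is a scheduled post-dose draw in the blinded period: 1 draw × 80 participants = 80 samples at most. Early-termination, unscheduled and repeat central draws add to this. They include draws up to Week 14 in participants kept on assigned treatment to confirm resolution (Appendix 1, footnote u). The documents give no rate of AST/ALT at or above 3 × ULN, so the number of affected participants cannot be derived.

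**Step 6. Whether another passage closes the gap**

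- Section 3.4.1.1 makes results available to the Sponsor but gives it no duty to screen for liver thresholds or alert the site.
- Section 6.10 permits additional tests, and non-central ones when results are urgent, but does not tell the site to obtain an unredacted bilirubin when AST/ALT rises.
- Appendix 2 asks for repeat total bilirubin but does not exempt the repeat from redaction.
- Section 3.4.1.2 allows unblinding for medical need, which reveals the assignment, not the bilirubin.
- The Hy's law listing and E-DISH plots in SAP 6.6.2 serve the final study report and do not reach the site during treatment.

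**The case against.** The strongest reply is that Appendix 2 nowhere requires the rule to be completed from the routine central report.

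- **Visible signal.** AST and ALT are not redacted, and Appendix 2 already asks for closer monitoring above 3 × ULN whatever the bilirubin. The Investigator can order further tests, locally if urgent.
- **Repeat testing comes first.** Appendix 2 treats a case as potential Hy's law, and so reportable, once repeat testing confirms the criteria and no other cause has been found. That work-up includes creatine kinase, gamma-glutamyl transferase and prothrombin time/INR, which are not in the scheduled panel. It can be argued that a specific instruction to repeat bilirubin overrides the general redaction.
- **Timing.** Week 12 ends the blinded period for most participants, so a repeat taken afterwards would normally fall in the open-label phase.
- **Chronic hemolysis.** In this population it complicates classification even with every value released.
- **Cost to the blind.** The existing triggers fire on falls in Hb or reticulocytes. A liver trigger could reveal an Hb rise or a bilirubin fall, which is more suggestive of active treatment.

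Much of this stands, and it rules out any claim that cases would be undetectable. It narrows the gap without closing it. The override is a reading, not something the protocol states; it would still leave the first bilirubin hidden and blinded-period repeats uncertain. Whether Week 12 values are released once open-label treatment starts is not stated either. A local bilirubin shows the Investigator the same kind of value that the redaction protects, so relying on that route does not protect the blind better than a controlled release of bilirubin.

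**Conclusion.** The concern holds as stated: during the blinded period the central report alone cannot complete the Appendix 2 rule, and no release trigger concerns the liver. This is a conflict between two provisions, since exact adherence to one withholds a value the other needs. It should be corrected, but the exposure is narrow: at most about 80 scheduled samples plus unscheduled, repeat and early-termination draws. The documents do not show that a case was missed.

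The conclusion rests on the protocol and SAP alone. A laboratory or safety manual not provided may contain a liver alert. If so, the protocol should refer to it.

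**What to change.** Add one item to the release list in 3.4.1.1, for example:

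*The redacted bilirubin and hemolysis results will also be communicated to the Investigator for any sample that meets the AST/ALT criterion of Appendix 2, and for the follow-up samples that Appendix 2 calls for.*

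This uses Appendix 2's existing thresholds, including those for raised baseline AST/ALT, and needs no new clinical cut-off. Releasing bilirubin alone would protect the blind better but leave the hemolysis element resting mainly on LDH, so the fuller release is preferable.

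The cost is one sentence and one central-laboratory reporting flag. For a few participants the released values may hint at assignment. Section 3.4.1.1 already accepts release without breaking the blind, and the ulcer measurements for the efficacy endpoints come from a central external reviewer (6.7). The outcome most open to influence is the exploratory, Investigator-rated CGI-C (6.12).

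As an editorial matter, align the Appendix 2 statement that LFTs are not routine monitoring with 6.10 and 6.10.2, which schedule them; no scheduled draw is lost because of it. SAP section 2 records that the study was terminated and its last visit completed, so the change applies to the protocol as written and to any later protocol that pairs this redaction rule with this liver appendix.
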